5.4 Subgroups

We plan to generate different effect estimates for (1) providers and staff, and (2) patients and are statistically powered to do so. We also plan to produce separate effect estimates for the following subgroups: adult vs adolescent patients, types of providers, low baseline C-SSRS score vs moderate to high baseline C-SSRS score, Hispanic vs non-Hispanic, female vs male, cisgender vs transgender or gender-nonconforming, heterosexual vs. homosexual, bisexual, or other; and urban vs rural; however, this study has not been specifically powered to identify differing treatment effects in each of these subgroups.

6 ENDPOINTS AND COVARIATES

6.1 Aim 2: Primary endpoint

The primary outcome is loneliness, measured at 6 months as a score using the NIH Toolbox Social Relationship Scales loneliness measure. The instrument results in an uncorrected standard score (T-score) as well as an age- and gender-corrected score for adults and for adolescent ages 8-17; higher scores indicate more loneliness. Analyses will be based on the age- and gender-corrected scores.

6.2 Secondary endpoints

- Secondary outcomes include suicide ideation; suicidal ideation and behavior will be measured as score at 6 months using the Columbia Suicide Severity Rating Scale (C-SSRS). Scores range from 0-6. Risk factors for suicide will be measured by the Interpersonal Needs Questionnaire (INQ-15). This survey measures feelings of perceived burdensomeness and thwarted belongingness; scores range from 15 to 105. The changes from baseline thwarted belongingness and perceived burdensomeness scales will be analyzed separately.
- Depression will be measured as score at 6 months in the Patient Health Questionnaire-9 (PHQ-9); this questionnaire results in a score between 0-27, with higher scores indicating worse depression. A score of 5-9 is considered minimal depression, 10-14 is considered mild major, 15-19 is moderate major, and ≥ 20 is severe major. Analysis will be based on the continuous score, with categories examined in exploratory/sensitivity analysis.

6.3 Exploratory endpoints

- Suicide attempts and lethal means will be summarized and compared across treatment arms. Questions will include the number of attempts and aborted attempts and lethal means.
- Psychological stress will be measured using the NIH Toolbox and assessed as change from baseline. This instrument results in a continuous T-score outcome.
- Changes in alcohol and illicit drug use will be described. Participants will be asked if they are current, ever, or never user of a variety of substances (tobacco, alcohol, marijuana, other illicit drugs), as well as the amount and frequency of use for current users. Participants will be asked about whether or not the amount they use has changed. Changes from baseline to 6 months in the current/ever/never question will be summarized for each substance, as well as reporting the number and percentage of participants with any increase or any decrease.
- The GAD-7 scale will be used to measure anxiety. Participants respond to seven items and receive possible scores of 0-21.
- Attendance at mental healthcare appointments will be measured as a dichotomous variable (yes/no) at 6 months through self-report.

6.4 Safety Outcomes

This protocol considers completed suicide, suicide attempts, and inpatient admission in the context of highly suicidal study participants as expected events. These will be routinely tracked as key safety outcomes. The following safety outcomes will be assessed for each participant at 6 months and reviewed by the Data and Safety Monitoring Board twice annually to determine whether the rate of safety outcomes differs by intervention arm:

- Death by suicide
- Attempted suicide
- Interrupted or aborted suicide attempt
- Psychiatric hospitalization for anxiety, depression, and/or suicidal ideation
- Medical hospitalization related to self-harm or attempted suicide
- Medical hospitalization related to unintentional overdose or substance use disorder

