6.1 Schedule of Activities

Table 1: Schedule of MHAPPS Trial Activities

	Aim 1: Timepoint 0	Aim 2: Time Point 1: 0 weeks	Aim 2 Time Point 2: 0-2 weeks	Aim 2 Time Point 3: 1 week – 6 months	Aim 2 Time Point 4: 6 months
Timepoints are relative to each study participant.					
Aim 1 Informed Consent/Assent and Survey	X				
Aim 2 Informed Consent/Assent and Enrollment		X			
Aim 2 Baseline Survey & Contact Sheet		X			
Randomization		X			
Phone call with Idaho Suicide Prevention Hotline (Hotline)			CC+ arm only		
Caring text messages (11 total) sent from Hotline				X	
Aim 2 Outcome Survey					X
Safety Outcomes Reporting			X	X	X

MHAPPS Trial Protocol

SLHS Applied Research

December 30,2020

[figure not shown]

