8.3.1 Suicidal ideation

Reduced suicidal ideation and behavior will be measured as change from baseline score at 6 months using the Columbia Suicide Severity Rating Scale (C-SSRS).¹⁰⁰⁻¹⁰³ C-SSRS is widely used in practice and research and has strong psychometric properties for use with both adult and adolescent populations, which are summarized in a *Supporting Evidence* document.¹⁰² The C-SSRS has been shown to be an effective tool to measure suicidality (diagnosis) and is sensitive to change over time, which allows measurement of the effect of treatment at 6 months.^{102,104}

The C-SSRS is available in a full-length version comprised of 11 yes/no questions plus 7 multiple choice questions and space to collect and record brief narrative explanations. An abbreviated screener version of the C-SSRS consists of 5 yes/no questions related to suicidal ideation and one two-part yes/no question related to suicidal behavior. Both the full-length and screener versions of the C-SSRS are available in a 'lifetime-recent' version (to establish a baseline) and a 'since last contact' version to be administered at follow-up visits. Two versions of the C-SSRS will be used for this study: C-SSRS Lifetime-Recent Screener (given at baseline, in accordance with standard of care at SLHS), and C-SSRS Since Last

Contact Screener (given at 6 months). In addition to using the C-SSRS Screeners at baseline and follow-up, the study will incorporate three items from the full-version of the C-SSRS that are not included in the screener version to measure: (1) Aborted or self-interrupted suicide attempts; (2) interrupted suicide attempts; and (3) actual suicide attempts at baseline, 6 months. Information on non-lethal self-harm, lethal means used for attempts or completions, and death by suicide will also be collected. Vital records will be used to measure suicide completion.

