11.3 Safety Outcomes

This protocol considers completed suicide, suicide attempts, and inpatient admission in the context of highly suicidal study participants as expected events. These will be routinely tracked as key safety outcomes. The following safety outcomes will be assessed for each participant at 3 and 6 months and reviewed by the Data and Safety Monitoring Board twice annually to determine whether the rate of safety outcomes differs by intervention arm:

- Death by suicide
- Attempted suicide
- Interrupted or aborted suicide attempt
- Psychiatric hospitalization for anxiety, depression, and/or suicidal ideation
- Medical hospitalization related to self-harm or attempted suicide
- Medical hospitalization related to unintentional overdose or substance use disorder

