11.4 Adverse Events and Serious Adverse Events

This protocol does not include tracking of adverse events (AEs). This protocol does not include real-time tracking of serious adverse events (SAEs) for several reasons. First, as stated above, the most important events that would be defined as SAEs are expected safety outcomes in the context of study participants experiencing suicidality or other forms of mental distress. All deaths of study participants will be reviewed and assessed to determine whether the cause of death is suicide. We do not anticipate any SAEs beyond those listed as safety outcomes above, but unanticipated SAEs that occur will be reviewed by the DSMB and the IRB. Second, this research compares two models of an evidence-based intervention that has been widely studied, has an established safety record, and is already in widespread

clinical practice. This is not an experimental, novel, or untested intervention with unknown safety outcomes. Finally, the most important safety question to ascertain in the context of this trial is whether rates of safety outcomes or SAEs are differential across the two intervention groups. This protocol will monitor safety outcomes collected at 6 months as part of routine study outcome assessments through regular DSMB meetings to ensure equal ascertainment of outcomes across intervention groups. This is the most valid and reliable way to review safety data in the context of this pragmatic clinical trial.

12. Data Collection & Management

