12.1 Data Collection

All data for this study will be collected via online REDCap surveys. *Table 2* includes a list of all study variables, which aim they are associated with, and which tool will be used for assessment.

Table 2: MHAPPS Trial Variables & Other Data Elements

Variables			
Outcomes	Tool	Survey Collected	Source
Loneliness	NIH Toolbox – Social Relationship Scales - Loneliness Scale	Aim 1 Survey; Aim 2 Outcome Survey	REDCap
Suicidal ideation & behavior	C-SSRS Screener	Aim 1 Survey; Aim 2 Outcome Survey	REDCap
Recent suicide attempts, suicide completion, & self-harm; lethal means	6-Months Suicide Attempts Survey	Aim 1 Survey; Aim 2 Outcome Survey	REDCap
Perceived Burdenomeness; Thwarted Belongingness	INQ-15	Aim 1 Survey; Aim 2 Outcome Survey	REDCap
Stress	NIH Toolbox – Perceived Stress 10	Aim 1 Survey; Aim 2 Outcome Survey	REDCap
Alcohol and Illicit drug use	Youth Risk Behavior Survey Questions	Aim 2 Baseline Survey; Aim 2 Outcome survey	REDCap
Depression	PHQ-9	Aim 1 Survey; Aim 2 Outcome Survey	REDCap
Anxiety	GAD-7	Aim 1 Survey; Aim 2 Outcome Survey	REDCap
Uptake of outpatient mental health treatment	N/A	Aim 2 Baseline Survey; Aim 2 Outcome Survey	REDCap
Exposure Variables		Survey Collected	Source
Date of birth, age in years, age category (adult/peds)		Aim 1 Survey	REDCap

MHAPPS Trial Protocol

SLHS Applied Research

December 30,2020

Sex at birth	Aim 1 Survey	REDCap
Race and ethnicity	Aim 1 Survey	REDCap
Zip code of residence (urban/rural)	Aim 1 Survey	REDCap
Gender identity & sexuality	Aim 2 Baseline Survey	REDCap
Religion	Aim 2 Baseline Survey	REDCap
Variables related to employment and occupation of self/parent	Aim 1 Survey	REDCap
Education / maternal education	Aim 1 Survey	REDCap
Living situation (permanent, temporary)	Aim 1 Survey	REDCap
Number of people at home	Aim 1 Survey	REDCap
Caregiving for dependent(s)	Aim 1 Survey	REDCap
Financial security and food security	Aim 1 Survey; Aim 2 Baseline Survey	REDCap
Food access and eating habits and COVID-19	Aim 2 Baseline Survey	REDCap
Physical activity and COVID-19	Aim 2 Baseline Survey	REDCap
Perceived risk for COVID-19 & other COVID-19-related questions	Aim 1 Survey; Aim 2 Outcome Survey	REDCap
Masking practices & beliefs	Aim 1 Survey; Aim 2 Outcome Survey	REDCap
Social distancing practices & beliefs	Aim 1 Survey; Aim 2 Outcome Survey	REDCap
School attendance, extracurricular activities	Aim 2 Baseline Survey (Youth)	REDCap

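### Three of the six safety outcomes are hospitalisations with no listed data item, and the safety proportion read literally counts 6-month non-responders as event-free

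*SAP*

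**What the plan says.** **The promise.** SAP 6.4 states: "The following safety outcomes will be assessed for each participant at 6 months and reviewed by the Data and Safety Monitoring Board twice annually". The stated purpose is to see whether rates differ by arm. Protocol 11.3 gives the same six outcomes. Three are admissions: "Psychiatric hospitalization for anxiety, depression, and/or suicidal ideation", medical admission after self-harm or an attempt, and "Medical hospitalization related to unintentional overdose or substance use disorder".

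**The data sources.** Protocol 12.1 says "All data for this study will be collected via online REDCap surveys" and that Table 2 "includes a list of all study variables, which aim they are associated with, and which tool will be used for assessment". SAP 4 says the same of its Table 1. Protocol 11.4 adds: "This protocol will monitor safety outcomes collected at 6 months as part of routine study outcome assessments". It also says that adverse events are not tracked and that serious adverse events are not tracked in real time. The schedule in Protocol 6.1 has a row headed "Safety Outcomes Reporting", with no source given.

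**The analysis.** SAP 5.3 (item 2b) defines the safety population as everyone who completed enrolment and the baseline survey. SAP 7.2.4 asks for counts and proportions of the listed events, and of any other reported events, by cohort and arm. SAP 7.3 imputes missing 6-month outcomes by hot deck and does not mention safety events. SAP 7.4 limits the missing-data sensitivity work to the primary results. SAP 5 plans for at least 70% retention.

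**The concern.** Protocol 11.4 rests its light safety system on one argument: the question that matters is whether safety rates differ between arms, and collection at 6 months gives equal ascertainment. That argument needs two things, and the text does not secure either.

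First, each of the six outcomes needs a data item. Admissions are left out of real-time SAE tracking because they count as expected safety outcomes. As safety outcomes, though, they have no listed item. If data collection follows the lists, three of the six rows in the DSMB table have no planned source, and an empty row could be read as zero events.

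Second, the proportion needs a rule for people whose status is unknown. The denominator is all enrolled with a baseline survey; the numerator, apart from death, comes from those who answer at 6 months. Dividing one by the other treats silence as absence of the event. This understates every rate and passes any difference in retention into the arm comparison. The DSMB may use these figures when it considers stopping early (Protocol 11.2).

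**Working it through.** **Step 1. Match the six outcomes to the lists.**

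| Safety outcome | Listed source |
|---|---|
| Death by suicide | Vital records; suicide attempts survey row |
| Attempted suicide | Suicide attempts survey; C-SSRS |
| Interrupted or aborted attempt | No row names it; committed to in Protocol 8.3.1 |
| Psychiatric admission | None found |
| Medical admission, self-harm or attempt | None found |
| Medical admission, overdose or substance use disorder | None found |

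The nearest rows are alcohol and drug use, outpatient treatment uptake and, in the Protocol only, access to care. Protocol 8.3.1 says "Information on non-lethal self-harm, lethal means used for attempts or completions, and death by suicide will also be collected", which does not extend to admission. The 6-month list in Protocol section 6 has six instruments and no admission item. Where the tables use a source other than the surveys, they name it (Mosio, vital records, CDC or state prevalence data); medical records are not among them. Protocol 16.9 mentions medical records only for inspection.

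**Step 2. Size of the unknown group.** The plan gives no safety event rate to reproduce. Its usable figures are 165 per arm in each of two populations (4 × 165 = 660) and at least 70% retained. Assuming all 660 complete the baseline survey, the number unknown at that minimum is 0.30 × 660 = 198, or 0.30 × 165 = 49.5 per arm per population. The 70% is a planning minimum, so the actual loss could be smaller or larger.

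**Step 3. Share of events seen if unknowns count as event-free.** Let r be retention and k the risk in non-responders relative to responders (assumed). Share seen = r / (r + (1 − r)k).

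| r | k = 1 | k = 2 | k = 3 |
|---|---|---|---|
| 0.70 | 0.70 | 0.7/1.3 = 0.54 | 0.7/1.6 = 0.44 |
| 0.80 | 0.80 | 0.8/1.2 = 0.67 | 0.8/1.4 = 0.57 |

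**Step 4. Effect on the arm comparison** (all rates and retention by arm are assumed).

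- Equal true risk of 5%, retention 80% in CC+ and 60% in CC, k = 1: 0.05 × 0.80 = 4.0% against 0.05 × 0.60 = 3.0%, ratio 1.33. In counts this is 6.6 against about 5.0 of 165.
- The same with k = 2: 0.05 × 0.8/1.2 = 3.33% against 0.05 × 0.6/1.4 = 2.14%, ratio 1.56.
- Retention 75% against 65%: ratio 1.15 (k = 1) or 1.25 (k = 2).
- Masking: true 8% in CC+ and 5% in CC, retention 60% and 80%, k = 1: 0.08 × 0.60 = 4.8% against 0.05 × 0.80 = 4.0%. A 3.0-point difference shows as 0.8.

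The ratios under equal true risk do not depend on the level of risk.

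**Step 5. Same data, different conventions.** Assume 3 events among 115 responders of 165. Over all enrolled: 3/165 = 1.8%. Over known status: 3/115 = 2.6%. If every unknown had the event: (3 + 50)/165 = 32.1%. SAP 7.2.4 does not say how the unknowns are to be treated.

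**Step 6. What a known-status denominator would do.** With k = 1 it recovers the true rates in Step 4. With k = 2 and retention of 80% against 60% it gives 0.05/1.2 = 4.17% against 0.05/1.4 = 3.57%, ratio 1.17 instead of 1.56. It reduces the distortion without removing it, so the unknown count must be shown beside it.

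**The case against.** The strongest reply is that a collection route is stated: both documents say the six outcomes will be assessed for each participant, and Protocol 11.4 places this in the 6-month assessment. The outcome survey is not supplied and may hold the items. The variable lists are also not fully exhaustive: interrupted and aborted attempts and baseline quality of life have no row either, and Mosio and vital records appear despite the statement that all data come by survey. This stands, and it limits the point. A reader might infer that participants were never asked about admissions, or that this part of the plan cannot be carried out. An unlisted item does not establish either.

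A reader might also infer that SAP 7.2.4 has no denominator, or that admissions enter the table only if volunteered. Both are wrong. SAP 5.3 fixes the denominator, and 7.2.4 covers the listed events, which include the admissions. The gap is only how unknown status is counted.

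It may be tempting to add that CC+ has an extra reporting channel through its call. The call is attempted only in the first two weeks, its safety check is conditional, and both arms can reply to texts through week 24. The point does not rest on this.

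Two further replies have some force. SAP 7.3 read broadly could cover missing safety answers, but neither 7.2.4 nor 7.3 says so. The DSMB reviews retention, data completeness and its reporting tables, and those tables may settle the convention; they are not in the documents. Finally, every rate and every arm-specific retention figure above is assumed.

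**Conclusion.** The point holds in two limited parts.

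1. Three of the six promised by-arm safety outcomes have no named item or record source in either variable table or in the 6-month assessment list, and no other adverse event system covers them. Whether an unlisted item exists cannot be settled from the documents.
2. The safety proportion, taken with its stated denominator, counts unknowns as event-free. At the planning minimum, about 198 of 660 would be unknown for everything except death. Rates would then show 70% of the true figure if non-responders carry the same risk, and less if their risk is higher. The arm ratio is distorted only if retention differs by arm: 1.33 at an assumed 80% against 60%, and 1.15 at 75% against 65%.

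Both parts concern safety reporting. No primary or secondary efficacy analysis is affected. The correction is still worth making, because the trial admits people with C-SSRS scores of 3 or more, and admissions not asked about at 6 months may be hard to recover later.

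**What to change.** 1. In the Aim 2 Outcome Survey, Protocol Table 2 and SAP Table 1, add three yes/no items covering the time since enrolment, or list them if they already exist: psychiatric admission for anxiety, depression or suicidal ideation; medical admission for self-harm or an attempt; medical admission for overdose or substance use disorder. Ask them identically in both arms.
2. In SAP 7.2.4, report for each event, by arm and population: number with the event, number with known status, number unknown, and percent among known status. Report deaths from vital records over all enrolled.
3. State that safety events are not hot-deck imputed. This is a choice, but hot-deck donors are responders, so imputing would assume that non-responders share their risk within each loneliness tertile.

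**Cost.** Three more questions in a survey described as up to 50 (Protocol 15.1), an IRB-approved amendment and a few table columns. Self-reported admissions carry recall error. Non-responders stay unknown: the table would show the gap without closing it.

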6.5 Covariates

Potential effect modifiers will be assessed and include age, sex, gender identity, sexuality, race/ethnicity, religion, employment, urban/rural residence, drug/alcohol use, suicidal ideation at baseline, baseline depression score, baseline anxiety score, baseline stress score, baseline quality of life, measures of socioeconomic status and/or other variables related to the specified outcomes of interest.

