13.1 General Analytic Approach

Aim 1: Descriptive statistics will be used to summarize cross sectional survey results as well as baseline demographic and other exposure variables. Linear regression models or generalized linear regression models GLM with robust standard errors will be used to assess the association between variables of interest.

Aim 2: The primary analysis will compare the effectiveness of the two interventions (CC+ and CC) delivered to two populations (patients and providers/staff), potential confounding, effect modification, and mediation will be handled through study design (e.g. use of randomization to assign individuals to interventions), and statistically through stratification (population). Other published studies related to Caring Contacts have shown that patient-centered outcomes such as suicidal ideation change over a 6-month period in response to receipt of these interventions.⁵¹

Analyses will be stratified for patients and providers/staff, modeling the effects of intervention separately in these population groups. There is very little evidence regarding the effect of Caring Contacts on healthcare workers, and we hypothesize that the magnitude of effect may differ by population group. Generating evidence of the effectiveness of Caring Contacts with and without an introductory phone call in healthcare workers is the primary goal of this heterogeneity of treatment effect (HTE) analysis. **Linear regression with robust standard errors will be used to determine whether the primary outcome differs between CC+ vs CC.**

Linear regression and GLM models will be used in the analysis of the secondary outcomes. Robust/sandwich standard errors will be used to allow for departures of the observed standard errors from classic model assumptions.

All data analyses will be completed using appropriate statistical software (such as R and R Studio, SPSS, Stata, SAS, Python, and/or Microsoft Excel). Statistical significance will be determined based on a type I error (alpha) of 0.05 (two-sided). Confidence intervals will be reported in addition to p-values.

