Variables will be measured through the Aim 1 survey or Aim 2 Baseline survey and reported using descriptive statistics. Potential effect modifiers will be assessed and include age, sex, gender identity, sexuality, race/ethnicity, religion, employment, urban/rural residence, drug/alcohol use, suicidal ideation at baseline, baseline depression score, baseline anxiety score, baseline stress score, baseline quality of life, measures of socioeconomic status and/or other variables related to the specified outcomes of interest. Data will be analyzed according to both an intention to treat protocol and per protocol received. Please see section 5.4 *Populations for Analyses* for further detail.

This study will report the distribution of key variables to facilitate assessment of the study's internal and external validity. At a minimum, this study will report the distribution of key variables within the analytic population (key variables are defined as those that are included in the causal diagram at the beginning of the *Research Design* section of this Research Plan). Missing data will be assessed on a regular basis through routine data reports. These reports will allow the investigators to assess the cause of missing or anomalous entries, and address these if possible. If missing values cannot be retrieved, the reason for the missingness will be recorded in data comments available through REDCap. Study staff will record the reason for any participant drop-out during the 6 months of follow-up.

[13.2 Power & Sample Size for Aim 2](#)

The total sample size for the aim 2 trial is 660 participants. For each stratum (patients, providers/staff), a sample of 330 subjects (165 in each arm) allows 80% power to detect a difference of 5 units in the primary outcome (loneliness) if a minimum of 70% of participants are retained through study completion.

[13.3 Duplicate Surveys](#)

A data cleaning step will be included to identify surveys completed twice by the same individual. This may occur, for example, when an individual is both a provider/staff person and a patient at SLHS. If duplicate surveys are identified, the first will be retained, and the second will be excluded from the research.

[13.4 Missing Data](#)

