7.2.3 Subgroups

The primary outcome will be summarized in subgroups defined by:

- Age category: older adult (50+) vs. adult (26-49) vs younger adult (18-25) vs adolescent patients (<18),
- types of providers (patient-facing providers [physicians and APP; pharmacy, PAS, lab, specialists, technicians, MAs;; nursing; social support services] vs. non-clinical [office work and educators; senior management; and other]),
- baseline suicide risk (low baseline C-SSRS score vs moderate to high baseline C-SSRS score),
- Hispanic vs non-Hispanic,
- female vs male sex at birth,
- cisgender vs transgender or gender-nonconforming,
- heterosexual vs. homosexual, bisexual, or other, and
- urban vs rural.

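### Separate subgroup estimates and an open-ended modifier list, with no treatment-by-factor interaction and no exploratory label, leave the subgroup results without a valid reading

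*SAP*

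**What the plan says.** SAP 6.5 states: "Potential effect modifiers will be assessed and include age, sex, gender identity, sexuality, race/ethnicity, religion", and continues to 15 named variables: age, sex, gender identity, sexuality, race/ethnicity, religion, employment, urban/rural residence, drug/alcohol use, and baseline suicidal ideation, depression, anxiety, stress, quality of life and socioeconomic status. It closes with an open item: "measures of socioeconomic status and/or other variables related to the specified outcomes of interest". Protocol 13.1 carries the same list. Neither section says how modification will be assessed.

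On subgroups, SAP 5.4 says "We also plan to produce separate effect estimates for the following subgroups", and Protocol 13.5 says the same. SAP 7.2.3 uses a weaker verb: "The primary outcome will be summarized in subgroups defined by". It then lists eight factors: age (four levels), provider type, baseline C-SSRS risk, Hispanic ethnicity, sex at birth, gender identity, sexuality and urban/rural residence. SAP 5.4 adds one caveat: "this study has not been specifically powered to identify differing treatment effects in each of these subgroups".

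SAP 7.2.1 fits the primary model separately in patients and in providers/staff, adjusting for the baseline score. The only rule on significance is in Protocol 13.1: "Statistical significance will be determined based on a type I error (alpha) of 0.05 (two-sided". The SAP states no alpha. It does use the word exploratory, but only for the endpoints in 6.3 and for the PHQ-9 categories in 6.2.

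**The concern.** A treatment estimate in each level, with no contrast between levels, invites the reading that the call helped in one group and not in another. That comparison of two p-values does not test whether the effects differ. The power caveat warns against reading a null subgroup as no effect. It says nothing about how to read a subgroup that reaches p<0.05.

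The open item in the modifier list lets variables be added after the data are seen, with nothing to mark them as later additions.

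The stake is practical. Protocol 8.1.1 says that how the interventions affect people in different occupations will matter for future implementation. A chance pattern could therefore influence who is offered the introductory call, or who is not.

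**Working it through.** **Inputs from the documents.** There are 330 participants per population, 165 per arm. Retention is 70%, so 0.7 × 330 = 231 completers, or 115.5 per arm. The target difference is 5 units at 80% power, and alpha is two-sided 0.05 (Protocol 13.1, as a general rule). There are 15 named modifiers and eight subgroup factors. Provider type does not apply to patients, so seven factors apply there and eight in staff.

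**The plan's own power figure.** It cannot be reproduced, because no SD is given. Back-solving, SD = 5 × √(115.5/2) / (1.960 + 0.842) ≈ 13.6. An SD of 10 would give 96.7% power, and 15 would give 71.7%.

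**Overlap of the two lists.** Each of the eight factors corresponds to one of the 15: age, employment, baseline suicidal ideation, race/ethnicity, sex, gender identity, sexuality and urban/rural residence. Seven named modifiers are left with no analysis in SAP 7.2: religion, drug/alcohol use, depression, anxiety, stress, quality of life and socioeconomic status.

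**Modifier tests, conditional on one test per modifier at 0.05 and no true effect.** For one population:

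- Independent tests: 1 − 0.95^15 = 0.537.
- Test statistics with common correlation 0.5 (assumed): 0.361.

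For two independent populations, 1 − (1 − p)²:

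- Independent: 1 − 0.463² = 0.785.
- Correlation 0.3: 0.706.
- Correlation 0.5: 1 − 0.639² = 0.592.

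If only the SAP 7.2.3 factors were tested by interaction (seven in patients, eight in staff), the two-population figure is 1 − 0.95^15 = 0.54 when independent and 0.42 at correlation 0.5.

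**Level-by-level estimates.** This is a simulation of 6,000 null trials per population with 231 completers, using t-tests in each level that has at least five per arm. The documents give no subgroup shares, so these are assumed. For patients: age 30/40/20/10, C-SSRS 80/20, Hispanic 13/87, sex 68/32, gender identity 95/5, sexuality 85/15, urban/rural 70/30. For staff: similar, with three age groups and provider type 70/30.

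| Event under no effect | Patients | Staff | Either |
|---|---|---|---|
| At least one level with p<0.05, either direction | 0.418 | 0.413 | 0.658 |
| Some factor with one level significant and another not | 0.414 | 0.407 | 0.653 |

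The first row combines as 1 − (1 − 0.418)(1 − 0.413) = 0.658. A repeat with a staff age split of 15/50/35 gave about 41%, 40% and 65%. Counting only levels significant in favour of CC+, it gave about 22% in patients and 21% in staff, so 1 − 0.78 × 0.79 ≈ 38% in either; with 21–23% in each population the combined figure is 38–39%. A simpler set-up with eight two-level factors gave 37.3% for one population in either direction. The two rows of the table nearly coincide: when a level reaches significance by chance, another level of the same factor almost always does not.

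**What an interaction test could detect.** For one 50/50 factor in one population, SE = SD × √(4/115.5 + 4/115.5). With SD 13.6 this is about 3.57. Power for a 5-unit difference in effects is Φ(5/3.57 − 1.96) ≈ 29%. With SD 10 it is 48%.

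**The case against.** The strongest reply is that the plan never commits to testing subgroups. SAP 7.2.3 says only that the outcome is summarised, the SAP has no alpha, and Protocol 13.1 asks for confidence intervals beside p-values. A reader might infer from the general alpha that every modifier and subgroup is to be tested at 0.05, but neither document says so. That part stands, and the error rates above are therefore conditional. What remains is that SAP 5.4 and Protocol 13.5 promise effect estimates, Protocol 13.1 exempts nothing from its significance rule, and no section says how the estimates are to be read.

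A reader might also add the lists into 15 plus eight. The eight lie within the 15, so that would double-count.

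It is also fair that the subgroup factors and their levels are prespecified. Protocol 13.1 separates the powered patient and staff estimates from the rest and names the healthcare-worker estimate as the main goal of the heterogeneity analysis. The statement that other subgroups are unpowered is a partial warning. It is not an exploratory label, and it does not supply the missing contrast between levels.

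**Conclusion.** The point holds as a defect of method and labelling. The plan estimates effects level by level, gives no test of whether they differ, leaves the modifier list open, and does not call these analyses exploratory. The primary analysis is untouched.

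Its size is conditional on results being read at two-sided 0.05 with no true difference. Under the assumed subgroup shares, at least one level is significant in about 40% of trials in one population and about 65% in either. For 15 modifier tests per population the chance of a false positive is 59–79%, for correlation from 0.5 down to zero; in one population alone it is 36–54%.

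A reader might infer that a null trial would more often than not produce a finding that CC+ works in some group. The figures do not support that. The 65% counts both directions, and restricted to results favouring CC+ it is 38–39% across both populations and 21–23% in each. With interaction power of about 29% at the implied SD, even correctly tested modifiers could be no more than exploratory here.

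**What to change.** - **SAP 7.2.3:** for each factor that applies to the population, add a treatment-by-factor interaction to the SAP 7.2.1 model. Report the difference in effects with its 95% CI beside the level estimates. For age, which has more than two levels, add a joint test.
- **SAP 5.4 and 7.2.3, Protocol 13.5:** state that these analyses are exploratory and that a within-level p<0.05 does not support a subgroup claim.
- **SAP 6.5 and Protocol 13.1:** make the modifier list agree with 7.2.3. Either restrict it to those factors, or keep the other seven named modifiers and put them under the same interaction method. Which to keep is the sponsor's choice. Removing only the open-ended phrase would leave those seven promised but without a method. If baseline quality of life stays, name its instrument, since none appears in Protocol Table 2 or SAP Table 1.
- Report any variable added later as post hoc.

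The cost is a few sentences and one interaction per factor, with no new participants and no change to the primary analysis. The downside is that modifiers outside the list can be reported only as post hoc.
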